### Number of Participants:

The approximate total number of evaluable participants will be up to [REDACTED], as shown below:

- Part 1 - Escalation Phase: Up to approximately [REDACTED] DLT-evaluable participants may be treated, including:
  - Part 1A - Safety Evaluation of BMS-986288 Monotherapy Escalation: Up to [REDACTED] evaluable participants
  - Part 1B - Safety Evaluation of BMS-986288 in Combination with Nivolumab: Up to [REDACTED] evaluable participants
  - [REDACTED] Evaluation of BMS-986288 as a Monotherapy and in Combination with Nivolumab: Up to [REDACTED] evaluable participants
- Part 2 - Initial Expansion Phase: Up to [REDACTED] evaluable participants may be treated, including:
  - Part 2A Cutaneous Melanoma - BMS-986288 [REDACTED] Cohort Expansion: Up to [REDACTED] participants with cutaneous melanoma
  - Part 2A NSCLC - BMS-986288 [REDACTED] Cohort Expansion: Up to [REDACTED] participants with NSCLC will be treated. If more than 1 dose level is evaluated, additional participants (up to [REDACTED] participants per dose level) may be enrolled, up to [REDACTED] participants (eg, [REDACTED] participants  $\times$  2 arms)
  - Part 2B - BMS-986288 in Combination with Nivolumab Cohort Expansion: Up to [REDACTED] participants with NSCLC will be treated. If more than 1 dose level is evaluated, additional participants (up to [REDACTED] participants per dose level) may be enrolled, up to [REDACTED] participants (eg, [REDACTED] participants  $\times$  2 arms)
  - Part 2C randomized MSS CRC cohort:
    - ◆ Arm C - BMS-986288 in combination with nivolumab: up to [REDACTED] participants will be treated.
    - ◆ Arm D - standard of care: up to [REDACTED] participants will be treated with regorafenib. Participants will have the option to transition to BMS-986288 in combination with nivolumab upon progression (Arm Z).
    - ◆ If more than 1 dose level is evaluated, additional participants (up to [REDACTED] participants) may be enrolled in a separate arm (Arm E) in Part 2C.

**Treatment Arms and Duration:**

Part 1: The Dose-Escalation Phase is where the dose of BMS-986288 will be administered IV alone (Part 1A) or in combination with nivolumab (Part 1B). [ ] administration of BMS-986288 as a monotherapy (Arm A) or in combination with nivolumab (Arm B) may also be evaluated [ ]

- The BMS-986288 Monotherapy Escalation (Part 1A) will escalate the dose of BMS-986288 to determine the monotherapy maximum tolerated dose (MTD)/recommended Phase 2 dose (RP2D). Specifically, the Part 1A dose escalation will evaluate different doses of BMS-986288 starting at [ ] mg, followed by [ ] [ ]. If it appears that a planned dose level is associated with an unacceptable frequency of toxicities, then an intermediate dose or alternative administration schedule may be evaluated, and will not initially exceed a dose determined to be tolerable. After preliminary evaluation of safety and PK data from these intermediate dose or alternative administration schedules, re-escalating doses of BMS-986288 may be initiated. The study will first evaluate the safety and tolerability of BMS-986288 monotherapy based on dose-limiting toxicities (DLTs), using a Bayesian Logistic Regression Model (BLRM) employing the escalation with overdose control (EWOC) principle, and overall assessment of available safety, PK, and pharmacodynamic data.
- The Safety Evaluation of BMS-986288 in Combination with Nivolumab (Part 1B) will evaluate the safety and tolerability of various doses of BMS-986288 in combination with nivolumab to determine the combination MTD/RP2D. Treatment in Part 1B will be initiated in a staggered manner relative to the BMS-986288 Monotherapy Escalation (Part 1A). Specifically, Part 1B can be initiated upon the decision to escalate when at least 2 dose levels in Part 1A have cleared the DLT period in accordance with dose escalation rules, after which dose escalation in Part 1A and Part 1B will proceed in parallel. At no point will the dose of BMS-986288 administered in combination with nivolumab in Part 1B exceed the highest safe dose in ongoing monotherapy dose escalation in Part 1A or the highest dose determined to be tolerated in Part 1A. In Part 1B, the dose of BMS-986288 will be escalated, whereas the dose of nivolumab will be [ ]. However, if it appears that a planned dose level is associated with an unacceptable frequency of toxicities, then an intermediate dose, additional cohorts of alternative BMS-986288 administration schedules, or de-escalating doses of nivolumab may be evaluated, and potential re-escalating doses of BMS-986288 may then be initiated. The safety and tolerability of the BMS-986288 combination with nivolumab will be evaluated using a BLRM-copula employing the EWOC principle, and an overall assessment of available safety, PK, and pharmacodynamic data.
- The [ ] Evaluation of BMS-986288 as a Monotherapy and/or in Combination with Nivolumab [ ] may be conducted to obtain preliminary data on the safety, tolerability, PK, bioavailability, and pharmacodynamics of BMS-986288 alone or in combination with nivolumab when [ ] will be initially composed of a single cohort for BMS-986288 monotherapy (Arm A) and/or BMS-986288 in combination with nivolumab (Arm B). The dose and administration schedule of BMS-986288 alone or in combination with nivolumab selected for [ ] will be determined by evaluation of the available clinical safety, PK, and pharmacodynamic data from Part 1A and Part 1B, [ ]. BMS-986288 may be combined with the [ ] depending on the dose selected (Arm A and/or Arm B). Nivolumab in combination with [ ] may also be administered (Arm B). The BMS-986288 dose in [ ] will not exceed the highest dose equivalent determined to be tolerated in Part 1A and/or Part 1B. [ ] may be used to inform [ ] dose selection in The Initial Expansion Phase (Part 2).

Part 2: The Expansion Phase is where cohorts of BMS-986288 [ ] (Part 2A) and Combination With Nivolumab (Part 2B) are expanded to gather additional safety, tolerability, preliminary efficacy, PK, and pharmacodynamic information in specific participant populations.

- One or more dose regimens of BMS-986288 alone and in combination with nivolumab selected for Part 2 cohort expansion will be selected from the range of doses assessed as tolerable in Part 1, and which do not exceed the MTD or highest dose administered. These dose(s) will be selected based on evaluating the recommendation from BLRM and an overall assessment of available safety, PK, pharmacodynamics, and efficacy data from Part 1.
- Part 2 is currently comprised of signal-seeking expansion cohorts in cutaneous melanoma, NSCLC, and a randomized MSS CRC cohort in comparison with regorafenib; additional tumors or potential arms will be included upon evaluation of available safety, PK, pharmacodynamic, and efficacy data from Part 1.

- In Part 2C, the efficacy and safety of BMS-986288 [REDACTED] with nivolumab will be assessed in participants with MSS CRC who have progressed or relapsed on at least 2 prior standard therapies. Participants must not have received prior anti-CTLA-4, anti-PD-(L)1 therapy in the advanced or metastatic setting. The dose(s) to be evaluated in Part 2C will be selected from the range of doses assessed as tolerable in Part 1B, and which do not exceed the MTD or highest dose administered that has cleared safety. The dose(s) will be selected based on the totality of available safety, tolerability, efficacy, PK, and PD data. Regardless of whether or not [REDACTED] status is known, all participants will be tested during screening for extended RAS (Kirsten rat sarcoma virus [KRAS] and [REDACTED] and [REDACTED] status. The Sponsor may elect to prioritize enrollment of participants based on [REDACTED] status as well as presence of liver metastasis at screening. In Part 2C, participants will be treated [REDACTED] for up to 2 calendar years regardless of treatment delays. This cohort will have a standard of care control arm using regorafenib at [REDACTED] mg, or in accordance with locally approved prescribing information, orally once daily for 21 days of each 28-day cycle.

**Study Treatment:** An overview of study treatment is shown in Table 2.

**Table 2: Study Treatment for CA043001**

Medication	Potency	IP/Non-IP
BMS-986288 Powder for Solution for Injection	[REDACTED] mg per vial	IP
Nivolumab (BMS-986558) Solution for Injection	[REDACTED] mg (10 mg/mL)	IP
[REDACTED] [REDACTED] [REDACTED]	[REDACTED] mg (1 mg/mL)	IP
Regorafenib Tablet b	40 mg c	IP

[figure not shown]
Abbreviations: IP = investigational product; [REDACTED]

b These products may be obtained by investigational sites as local commercial product in certain countries if allowed by local regulations. In these cases, products may be a different pack size/potency than listed in the table. These products should be prepared/stored/administered in accordance with the package insert or SmPC.

c May include other commercially available strengths.

The study design schematics are shown in [Figure 1](#) and [Figure 2](#).

**Figure 1: Study Design Schematic**

[figure not shown]
Abbreviations: 3L/4L = 3rd/4th line; BMS = Bristol-Myers Squibb; CRC = colorectal cancer; CTLA-4 = cytotoxic T-lymphocyte-associated protein 4; IRT = Interactive Response Technology; IV = intravenous; MSS = microsatellite stable; NSCLC = non-small cell lung cancer; PK = pharmacokinetics; [REDACTED] RCC = renal cell carcinoma; [REDACTED] RP2D = recommended Phase 2 dose; [REDACTED]; SCCHN = squamous cell carcinoma of the head and neck; TBD = to be determined; TNBC = triple-negative breast cancer.

- a Prior anti-PD-(L)1 therapy allowed. Anti-CTLA-4 naive required.
- b Additional doses and dose schedules may be explored using data obtained from [REDACTED] administration.
- c Part 1B will not start until demonstration of acceptable safety in at least 2 cohorts from Part 1A. Subsequently, treatment in both parts will occur in parallel.
- d Doses(s) will be identified upon clinical evaluation of available safety, PK, pharmacodynamics, and efficacy data in Part 1A and/or Part 1B. [REDACTED] may be used in combination with BMS-986288 or nivolumab, depending on the determined dose. Details will be provided through a protocol amendment.
- e Part 2 will be initiated upon evaluation of available safety, PK, pharmacodynamics, and efficacy data from Part 1 and may include IV or [REDACTED] administration.

f Alternative assignment: In Part 2A [REDACTED] and Part 2B Combination Expansion, Part 2A and Part 2B may be open concurrently. In this case, treatment assignments will alternate between Part 2A and Part 2B. Multiple doses may be open concurrently in each part. In that case, treatment assignments will alternate between the dose levels, with consecutively treated participants assigned to different parts through IRT whenever possible. If there are no openings available in the dose level to which the participant would be assigned by this algorithm, then the participant will be assigned to the next open dose.

g Intermediate dose level.

**Figure 2:** Study Design Schematic for Expansion Part 2C

Abbreviations: 3L/4L = 3rd/4th line; BICR = blinded independent central review; CRC = colorectal cancer; IRT, Interactive Response Technology; MSS = microsatellite stable; [REDACTED].

a Efficacy analyses based on the treated population may be performed for interim analyses.

b Stratification by liver metastasis status and a cap of 50% participants with liver metastases in each arm. Once enrolled in IRT, participants who have met all eligibility criteria for Part 2C will be randomized in a 2:1 ratio to nivolumab in combination with BMS-986288 (Arm C) or regorafenib (Arm D) and stratified by liver metastasis status. An additional dose of BMS-986288 ([REDACTED] mg or [REDACTED] mg) in combination with nivolumab may be opened as Arm E.

[REDACTED]

**Screening:** The screening period will be up to 30 days and begins by establishing the participant's initial eligibility and signing of the informed consent form. Within a given disease type, participants meeting all eligibility criteria will be enrolled in the study using an Interactive Response Technology according to the part and treatment arm availability.

**Treatment:** The initial dosing regimen of BMS-986288 is [REDACTED]. All participants will be treated for up to 2 calendar years. Continuous safety evaluation and tumor assessment occurring in Part 1 and Part 2 [REDACTED] of treatment and then [REDACTED] thereafter), will guide the decision to treat a participant with additional cycles of study therapy if the participant has confirmed clinical benefit (up to a maximum of 2 years).

- For the BMS-986288 Monotherapy Escalation (Part 1A) and the Expansion Phase BMS-986288 [REDACTED] (Part 2A), BMS-986288 will be infused over approximately 30 minutes.
  - Shorter infusion times may be used for the initial dose cohorts and longer infusion times (approximately [REDACTED]) may be used for the higher dose levels.
- For the Safety Evaluation of BMS-986288 in Combination with Nivolumab (Part 1B) and the Expansion Phase BMS-986288 in Combination with Nivolumab (Part 2B and Part 2C Arm C, Arm E, and Arm Z), BMS-986288 and nivolumab will each be infused over approximately 30 minutes.
  - When both BMS-986288 and nivolumab are given in combination, nivolumab will be given first, over [REDACTED] followed by BMS-986288 [REDACTED], beginning at least 30 minutes after completion of the infusion of nivolumab.
  - Shorter infusion times for BMS-986288 may be used for the initial dose cohorts and longer infusion times [REDACTED] may be used for the higher dose levels.
- Depending on the dose(s) selected for the [REDACTED] Evaluation of BMS-986288 as a Monotherapy and/or in Combination with Nivolumab [REDACTED] BMS-986288 and nivolumab may each be [REDACTED] with the [REDACTED].
  - [REDACTED] of study treatment should be administered [REDACTED]. Different sites should be used if both BMS-986288 [REDACTED] and nivolumab [REDACTED] are being administered (Arm B), with nivolumab being given first, followed by BMS-986288. [REDACTED] should not occur into or around an infected or acutely inflamed area because of the danger of spreading a localized infection. Clinical judgement should be used in determining the best site for [REDACTED] drug administration.
- For the [REDACTED] BMS-986288 in combination with nivolumab portion of the study, participants will receive the [REDACTED] dose of [REDACTED] mg [REDACTED] with the selected BMS-986288 dose [REDACTED] administration will be permitted when [REDACTED] is not possible upon confirmation with the Sponsor. [REDACTED] the infusion will be the same as described below). The starting dose will be [REDACTED] mg of BMS-986288. A possible additional arm with a to-be-determined dose of BMS-986288 may be added based on an evaluation of the entirety of the safety, PK, PD, and anti-tumor activity data from Part 1B. When both BMS-986288 and nivolumab are given in [REDACTED], the infusion will be given approximately over [REDACTED]. For participants weighing < 40 kg, the total infusion volume will be limited to 80 mL. For the [REDACTED] Arm D, the participants will receive regorafenib at [REDACTED] mg orally once daily for 21 days of each [REDACTED]-day cycle until disease progression, toxicity, withdrawal of consent, or death, whichever occurs first.
- Refer to the Pharmacy Manual for additional dose preparation details for BMS-986288, nivolumab, [REDACTED], and regorafenib (if applicable).
- Tumor progression and response endpoints will be assessed using RECIST v1.1.

#### Follow-up:

- Safety Follow-up Period:
  - Upon completion of study therapy (up to a maximum of 2 years, if applicable) or once the decision is made to discontinue the participant from treatment, that is, at EOT, all participants will enter a Safety Follow-up Period.
  - All participants will be evaluated for any new AEs for at least 100 days after the EOT visit. Follow-up visits should occur at Days 30, 60, and 100 ( $\pm$  7 days for all study visits) after the EOT visit. All participants should

complete the 3 clinical safety follow-up visits regardless of whether new anti-cancer therapy is started, except those participants who will withdraw consent for study participation.

- Imaging Follow-up Period:
  - Participants will continue to have radiologic and clinical tumor assessments after treatment discontinuation. Imaging assessments will continue to occur [REDACTED] ( $\pm$  1 week) from the date of first treatment until Week 48, then continue [REDACTED] ( $\pm$  1 week) thereafter. The duration of the Imaging Follow-up Period will be for a total of 2 years following EOT, or until initiation of another anti-cancer treatment, or death, whichever occurs first. Radiological assessments for participants who have ongoing clinical benefit may continue to be collected after participants complete the Survival Follow-up Period of the study. Participants who have disease progression after an initial course of study therapy will be evaluated beyond the EOT visit and will be allowed to receive other tumor-directed therapy as required.
- Survival Follow-up Period:
  - In parallel with the Safety Follow-up Period, all participants will start the Survival Follow-up Period. Participants will be followed by telephone Q12W ( $\pm$  2 weeks) from EOT for 2 years or until death, loss to follow-up, withdrawal of consent, or conclusion of the study, whichever comes first. Participants will have both the Imaging Follow-up Period and Survival Follow-up Period occur simultaneously. The duration of this follow-up is up to 2 years after EOT, although a longer follow-up period could be considered in selected cases if an efficacy signal is apparent. Subsequent therapies will also be recorded in this Survival Follow-up Period.

**Data Monitoring Committee:** No.

BMS has developed a multi-layered process to ensure safety monitoring through close collaboration of study site Investigators, the BMS study team, and the BMS Worldwide Patient Safety (WWPS)-led Safety Management Team (SMT). This collaborative process constitutes the Data Safety Monitoring Plan for the study. To support safety oversight, BMS has established ongoing processes for collection, review, analysis, and submission of individual adverse event reports and their aggregate analyses. Because this is an open-label study, WWPS, the BMS Medical Monitor, and the Investigators will have access to all data necessary for safety evaluation.

BMS WWPS is an internal group that operates independently from the clinical team to monitor safety across all BMS protocols, and analyze all data in an unblinded fashion. Within BMS, an SMT is established for investigational therapies under clinical development, and a member of WWPS chairs this team. In addition, signal detection is performed at least monthly and ad hoc throughout the study by the SMT composed, at a minimum, of the WWPS medical safety assessment physician (Chairman of the SMT) and WWPS single-case review physician, the study Medical Monitor(s) (or designee), the study biostatistician, and epidemiologist, all of whom analyze the data in an unblinded fashion. Furthermore, the SMT routinely monitors for actual or potential issues related to participant safety that could result in a significant change in the medical benefit-risk balance associated with the use of study treatment(s).

## **2 SCHEDULE OF ACTIVITIES**

Study assessments and procedures are shown in [Table 2-1](#), [Table 2-2](#), and [Table 2-3](#).

In limited instances, scheduled events (including events other than safety assessments) can occur outside of the indicated timeframes but the Sponsor should first be notified.

If a participant has a delay in study drug administration for any reason, then assessments and laboratory tests (with the exception of any tests needed to ensure participant safety) should be correspondingly delayed, with the exception of tumor assessments. Tumor assessments continue per protocol schedule regardless of any treatment delay incurred.

The pharmacokinetic (PK), pharmacodynamic, and safety profiles of BMS-986288 are being elucidated; modifications to the procedures (ie, reduction in PK, pharmacodynamic sampling, timing of procedures, dose schedules) currently outlined in Section 2 and [Section 9](#) may be required. These modifications will not include the addition of new procedures and will be documented in a note to file or administrative letter.

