For Part 1, 2A, 2B Exploratory 
 
To explore the potential association between anti-tumor activity and pharmacodynamic markers, such as, but not limited to, [REDACTED] prior to treatment and following administration of BMS-986288 alone and in combination with nivolumab
 
To explore the associations between BMS-986288 PK, safety, efficacy, and clinical biomarkers
 
To characterize the immunogenicity of BMS-986288 and nivolumab
 
To assess the preliminary efficacy of BMS-986288 alone and in combination with nivolumab in select advanced solid tumors using iRECIST
 
To assess the OS in participants treated with BMS-986288 alone and in combination with nivolumab
 
To assess the potential effect of BMS-986288 when administered [REDACTED] on the QTc interval
 
To characterize the PK and bioavailability of BMS-986288 when administered [REDACTED]
 
To explore the impact of treatment on NSCLC participant-reported symptoms and health-related quality of life (Part 2A and Part 2B only)
 
To explore participant overall perception of bother in relation to treatment-related symptomatic side effects (Part 2A and Part 2B only)
 
To explore overall health status (Part 2A and Part 2B only)
 
To measure [REDACTED], and assess [REDACTED] change over time and in association with response
 
	
 
Summary measures of anti-tumor activity by pretreatment level of biomarkers of interest; correlation/measure of association of anti-tumor activity and change (or % change) from baseline in biomarkers of interest
 
Association measures between BMS-986288 PK levels by [REDACTED] select outcomes, and biomarkers of interest
 
Incidence of ADA to nivolumab and BMS-986288
 
ORR, DOR, and PFS per iRECIST by BICR
 
OSR at 1 year and 2 years
 
Summary measures of ECG parameters and changes in QTcF (<math>\Delta</math>QTcF) from baseline
 
Summary of PK parameters when BMS-986288 is administered [REDACTED] alone or in combination with nivolumab
 
Mean NSCLC-SAQ scores and change from baseline scores
 
Proportion of participants endorsing each response option of the FACIT GP5
 
Mean EQ-5D-5L utility index scores and EQ-5D-VAS scores and change from baseline scores
 
Summary measures of [REDACTED] and correlation/ measure of association of anti-tumor activity and change (or % change) from baseline in [REDACTED]
 

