NSCLC-SAQ	X				X				X	X	Clinical outcomes assessments to be administered in Part 2A and Part 2B only. NSCLC-SAQ will only be administered to NSCLC participants. Data will be collected using electronic devices. See Section 9.1.2.														
FACIT GP5	X	X	X	X	X	X	X	X	X	X															
EQ-5D-5L	X				X				X	X															

Abbreviations: ADA = anti-drug antibody; BMS = Bristol-Myers Squibb; C = cycle; CT = computed tomography; CXDY = Cycle X Day Y, as an example; D = day; DLT = dose-limiting toxicity; ECG = electrocardiogram; ECOG = Eastern Cooperative Oncology Group; EOI = end of infusion; EOT = end of treatment; EQ-5D-5L = 5-Level EQ-5D; FACIT GP5 = Functional Assessment of Chronic Illness Therapy, General Physical item; hCG = human chorionic gonadotropin; IgG = immunoglobulin G; MRI = magnetic resonance imaging; NSCLC = non-small cell lung cancer; NSCLC-SAQ = Non-small Cell Lung Cancer Symptom Assessment Questionnaire; PD = progressive disease; PE = physical examination; PK = pharmacokinetic; █ RECIST = Response Evaluation Criteria in Solid Tumors; █ SAE = serious adverse event; SARS-CoV-2 = severe acute respiratory syndrome coronavirus 2; █ TNBC = triple-negative breast cancer; WOCBP = women of childbearing potential.

- a EOT is defined as the visit where the decision is made to discontinue the participant from treatment. Evaluations will be performed prior to study discharge, or for participants who are prematurely discontinued.
- b For participants who complete all scheduled cycles of therapy, the EOT visit will be the same as the last scheduled and completed on-treatment visit (eg, C26D1) and the start of the safety follow-up period. For participants who do not complete all scheduled cycles of therapy, the EOT visit will be the most recent on-treatment visit (with all available safety and response data); it does not need to be repeated and will be considered as the start of the safety follow-up period.
- c [REDACTED]

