#### **7.4.3 Dose Delays Due to Toxicity**

If an event is attributed to BMS-986288 or nivolumab, alone or in combination, then all study drugs must be delayed until treatment can resume (see [Section 7.4.3.1](#)). Delay administration of both nivolumab and BMS-986288 if any of the delay criteria in [Table 7.4.3.1-1](#) are met. Tumor assessments for all participants should continue per protocol even if dosing is delayed.

Participants who experience the following must have all study treatment(s) withheld:

- Potential DLTs, until DLT relatedness is defined.
- Drug-related select AEs and laboratory abnormalities in Table 7.4.3.1-1.
- AE, laboratory abnormality, or concurrent illness that, in the judgment of the Investigator, warrants delaying study treatment administration.
- Confirmed SARS-CoV-2 infection.

Participants who require a delay of study drug should be re-evaluated weekly or more frequently if clinically indicated. For participants receiving a combination (eg, Part 1B, [REDACTED], Part 2B), if dosing is delayed, then study drugs must be delayed together. If dosing with both study drugs is to be resumed after a delay, then both must be resumed on the same day. Criteria for participants who are required to permanently discontinue study treatments are listed in [Section 8.2](#). In addition,

all AEs should be evaluated and managed per the toxicity management algorithms in [Appendix 6](#). Participants not meeting guidelines for permanent discontinuation will be permitted to resume therapy based on the criteria specified below in Section 7.4.3.1. Participants eligible to resume study therapy will resume study therapy at the nominal treatment visit after their last received study medication dose.

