#### **7.4.3.1 Criteria to Resume Treatment**

Subsequent dosing with study therapy may resume once drug-related non-DLT AEs resolve to Grade 1 or baseline. When criteria to resume treatment are met, resume both nivolumab and BMS-986288 on the same day.

- Participants experiencing AEs not meeting criteria for permanent discontinuation may resume treatment with study intervention(s) if they have completed AE management (eg, corticosteroid taper) or are on  $\leq$  10 mg prednisone or equivalent and meet the requirements per [Table 7.4.3.1-1](#).
- Prior to re-initiating treatment in a participant with a dosing delay lasting  $>$  8 weeks (unless the exceptions in [Table 7.4.3.1-1](#) are met), the Medical Monitor (or designee) must be consulted. Continue tumor assessments per protocol even if dosing is delayed. Continue periodic study visits to assess safety and laboratory studies [REDACTED] or more frequently if clinically indicated during such dosing delays.
- Participants with confirmed SARS-CoV-2 infection may resume treatment after 1) at least 10 days (20 days for severe/critical illness) have passed since symptoms first appeared, positive RT-PCR test result, or positive viral antigen test result, 2) resolution of acute symptoms (including at least 24 hours has passed since last fever without fever reducing medications), 3) evaluation by the Investigator with confirmation that there are no sequelae that would place the participant at a higher risk of receiving investigational treatment, and 4) consultation by the medical monitor. For suspected cases, treatment may also resume if SARS-CoV-2 infection is ruled-out and other criteria to resume treatment are met.
  - Prior to re-initiating on-study treatment in a participant with a dosing delay lasting  $>$  8 weeks due to SARS-CoV-2 infection, the medical monitor/designee must be consulted.

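### Questionnaires move with a delayed dose, so a FACIT GP5 form due during a toxicity hold is usually answered after recovery, which tends to understate side-effect bother in Parts 2A and 2B

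*Combined protocol and SAP*

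**What the plan says.** The opening text of Section 2 (Schedule of Activities) ties the assessment calendar to dosing. Whatever the reason for a delay, "assessments and laboratory tests (with the exception of any tests needed to ensure participant safety) should be correspondingly delayed". The same sentence adds a second exception: "should be correspondingly delayed, with the exception of tumor assessments". No other category is exempt.

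Table 2-2 lists NSCLC-SAQ, FACIT GP5 and EQ-5D-5L under their own block, separate from the safety assessments, with the note "Clinical outcomes assessments to be administered in Part 2A and Part 2B only". FACIT GP5 is marked at every visit in Cycles 1 and 2. From Cycle 3, all three instruments are on Day 1 and at end of treatment. The GP5 endpoint in Table 1 and Table 4-1 is "Proportion of participants endorsing each response option of the FACIT GP5", and it is exploratory.

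On holds for toxicity, Section 7.4.3.1 says: "Subsequent dosing with study therapy may resume once drug-related non-DLT AEs resolve to Grade 1 or baseline". During the hold, Section 7.4.3 asks for contact: "Participants who require a delay of study drug should be re-evaluated weekly or more frequently if clinically indicated". For delays beyond 8 weeks, Section 7.4.3.1 adds: "Continue periodic study visits to assess safety and laboratory studies". None of these passages mentions a questionnaire. Sections 9.1.2 and 10.3.7 contain no rule for forms that fall due during a delay; the analysis is left to a statistical analysis plan still to be written.

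**The concern.** FACIT GP5 is in the study to record how much participants are bothered by side effects (Section 9.1.2.3). Under the Section 2 rule, its collection is postponed when side effects are bad enough to hold treatment, and it resumes when they have eased. The timing of measurement then depends on the quantity being measured. A response recorded at resumption describes a different state from the one at the planned time. An analysis plan can relabel the late form by its actual date, but it cannot supply an answer that was never collected during the hold.

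Tumor assessments are kept on their own schedule through any treatment delay. The questionnaires do not have that protection.

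**Working it through.** The plan states no figure for the questionnaires, so there is nothing to reproduce. The check is a trace of the text, a count, and an illustrative calculation.

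**Trace.**
1. A drug-related event listed in Table 7.4.3.1-1 for dose delay leads to a hold (Section 7.4.3).
2. Section 2 moves assessments with the dose, except safety tests and tumor assessments.
3. Questionnaires are not safety tests. Table 2-2 lists them apart from safety assessments, and Section 9.4 bases safety assessment on adverse events, vital signs, ECGs, physical examinations and laboratory tests.
4. Dosing generally resumes at Grade 1 or baseline (Section 7.4.3.1), so the displaced Day 1 form is completed at that point.
5. NSCLC-SAQ has a 7-day recall (Section 9.1.2.1), so a form completed at resumption does not reach back over a longer hold.
6. Section 2 lets scheduled events occur off schedule in limited instances after the Sponsor is notified. That permits a form during a hold but does not require one.

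**Count of required forms during a hold.** Cycle length is redacted, so assume 4 weeks. For a hold of L weeks starting at a due Day 1, a calendar schedule would place L/4, rounded up, Day 1 sets inside the hold. That is 1 set for 1 to 4 weeks and 2 sets for 5 to 8 weeks. Sections 7.4.4 and 8.1 require discontinuation beyond 8 weeks from the previous dose, with exceptions. Under Section 2 as written, the required number is 0.

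**Illustrative size for FACIT GP5.** Every input is an assumption:
- f, the share of Day 1 forms falling due in a toxicity hold: 0.10 to 0.30
- p_tox, the proportion highly bothered during the toxicity: 0.40 to 0.60
- p_rec, the proportion highly bothered at resumption: 0.10 to 0.15

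Understatement in Day 1 forms = f × (p_tox − p_rec).
- Smallest: 0.10 × (0.40 − 0.15) = 0.025, or 2.5 points
- Middle: 0.20 × (0.50 − 0.10) = 0.080, or 8 points
- Largest: 0.30 × (0.60 − 0.10) = 0.150, or 15 points

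Among the held forms alone, the difference is 0.40 − 0.15 = 25 points to 0.60 − 0.10 = 50 points.

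A second set of assumptions takes f from 0.05 to 0.30, with p_tox and p_rec of 0.6 and 0.3, or 0.8 and 0.2. It gives 0.05 × 0.3 = 1.5 points to 0.30 × 0.6 = 18 points. The result depends on the inputs, and the documents do not narrow them.

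**The case against.** The case for leaving the rule alone has real content, and most of it limits the reach of the point.

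- **Many severe toxicities end treatment rather than delay it.** Drug-related events meeting DLT criteria, and most Grade 4 events in Table 7.4.3.1-1, lead to discontinuation, with listed exceptions. Those participants have forms scheduled at end of treatment and at 30, 60 and 100 days (Tables 2-2 and 2-3). Footnote b of Table 2-2 lets the latest on-treatment visit serve as end of treatment, but the follow-up forms remain. This stands: the gap concerns participants who resume.
- **Early toxicity is partly captured.** GP5 is weekly in Cycles 1 and 2, and Section 5.5.1 gives a median onset of 4.6 weeks for Grade 2-4 immune-related events with ipilimumab. Forms due before a missed dose stay on schedule. If Cycle 2 Day 1 is itself held, however, the later Cycle 2 forms move with it.
- **Not every hold means bother.** Some holds are for laboratory values or SARS-CoV-2 infection. This is a reason to keep f modest.
- **Safety reporting is unaffected.** Adverse events are collected continuously, and they carry the primary objective of these parts.

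A reader might draw three stronger inferences that the documents do not support. The first is that symptoms and general health are understated too. NSCLC-SAQ covers cough, pain, dyspnea, fatigue and appetite, which could worsen while treatment is held, and nothing fixes a direction for EQ-5D-5L. The second is that the bias is largest in the more toxic regimen and shrinks a difference between Parts 2A and 2B. No such questionnaire comparison is planned, and the discontinuation rules remove many of the worst cases from the mechanism. The third is that forms are always completed after full recovery. Dosing may resume with Grade 1 symptoms, with an endocrinopathy controlled on replacement, or with limited residual rash.

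**Conclusion.** The point holds in a limited form. Followed as written, Section 2 moves a FACIT GP5 form due during a toxicity hold to the resumption visit, usually after recovery to Grade 1 or baseline. No other passage requires a form during the hold. For participants who resume, mainly from Cycle 3, this tends to understate side-effect bother. For NSCLC-SAQ and EQ-5D-5L, the supportable statement is that timing is shifted; the direction of any bias is open.

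The 2.5 to 15 point range is conditional on the assumed inputs and applies to Day 1 forms, not to all GP5 forms, since the weekly forms of Cycles 1 and 2 dilute it. The endpoint is exploratory and descriptive, and confined to Parts 2A and 2B. This is an inexpensive improvement to the data and does not threaten the study's main conclusions.

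**What to change.** In Section 2, extend the exemption already given to tumor assessments so that clinical outcomes assessments are completed on the planned calendar day counted from C1D1, whether or not study drug is given. Put the matching note in Table 2-2 and in the on-treatment schedules of Appendix 8. In the statistical analysis plan, summarise scores by time from first dose.

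Do not add extra GP5 forms only during toxicity holds, for example at the weekly re-evaluations. The number of forms would then depend on toxicity, and bad weeks would be over-represented unless this were modelled.

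The cost is a few questionnaires completed away from dosing visits, on the electronic devices already in use, and a small change to visit mapping in the analysis. No dosing, hold or resumption rule changes.
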